1.5 Total trial duration

Patient accrual was expected to be completed within 3 years including a run-in-period of 3 months. The total trial duration would be approximately 7.5 years including the 36 months recruitment period. Patients would be followed until death – thus follow-up was estimated to last up to 4.5 years following the enrolment of the last patient.

The trial will end with the preparation of the final report, initially scheduled for 7.5 years after the inclusion of the first patient. However due to premature accrual closure the final report will be prepared earlier, expected approximately 4.5 years after the inclusion of the first patient.

1.6 Previous protocol version (original protocol)

STIMULI trial, original protocol v1.0, was activated in December 2013 and the first patient was enrolled on the 28th of July 2014.

The low accrual rate experienced in the first few months of the STIMULI study, along with recently presented results showing significant benefits with Nivolumab treatment with or without Ipilimumab [Antonia S.J., JCO 2015; Larkin J., NEJM 2015; Postow M.A., NEJM 2015], led the protocol team to decide to proceed to protocol amendment (AM1). The protocol amendment has been completed and distributed to the sites (21st of September 2015) for submission to the corresponding authorities. The first subject was enrolled under AM1 on the 18th of December 2015.

The main modifications introduced by the amendment were:

the addition of Nivolumab to consolidation therapy

• the addition of carboplatin to standard therapy as an alternative to cisplatin

- addition of PFS as co-primary endpoint
- the option of contrast enhanced CT of the brain as an alternative to MRI at screening
- allowing one cycle of chemotherapy before enrolment of patient.

2 Statistical considerations for final analysis

2.1 Analysis timing

According to the modified statistical design, the final efficacy analysis will be performed when the 81 required PFS events have been observed among all STIMULI patients randomized under AM1.

2.2 Study's endpoints

2.2.1 Primary endpoint

The primary endpoint of the analysis is PFS, defined as the time from the **date of randomization** until documented progression (based on RECIST 1.1 criteria) or death, if progression is not documented. Censoring (patients without progression/death) for PFS will occur at the last tumour assessment. In the frame of a sensitivity analysis, if the last tumour assessment is «Non evaluable», censoring will occur to the more recent tumour assessment where an overall evaluable result is recorded.

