#### After randomisation:

For both treatment arms, post randomisation CT scans of thorax and upper abdomen will be repeated according to the schedule indicated below, until tumour progression:

- up to 18 months: every 9 weeks 9, 18, 27, 36, 45, 54, 63, 72, 81 (+/- 1 week)
- up to 2 years: every 12 weeks 93, 105 (+/- 1 week)
- years 3 and 4: every 6 months (26 weeks) 131, 157, 183, 209 (+/- 1 week)
- at 5 years: 260 (+/- 1 week)

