### 13.3. Determination of time point response

**Table 15: Determination of time point response**

Target lesions	Non-target lesions	New lesions	Overall response
CR	CR	No	CR
CR	Non-CR / non-PD	No	PR
CR	Not evaluated	No	PR
PR	Non-PD or not all evaluated	No	PR
SD	Non-PD or not all evaluated	No	SD

Target lesions	Non-target lesions	New lesions	Overall response
Not all evaluated	Non-PD	No	NE unless the sum of diam. of evaluated lesions in- dicates PD 
PD	Any	Yes or no	PD
Any	PD	Yes or no	PD
Any	Any	Yes	PD

- 1) From ref. 1 in appendix 2, p.234: When no imaging/measurement is done at all at a particular time point, the patient is not evaluable (NE) at that time point. If only a subset of lesion measurements are made at an assessment, usually the case is also considered NE at that time point, unless a convincing argument can be made that the contribution of the individual missing lesion(s) would not change the assigned time point response. This would be most likely to happen in the case of PD. For example, if a patient had a baseline sum of 50 mm with 3 measured lesions and at follow-up only 2 lesions were assessed, but those gave a sum of 80 mm, the patient will have achieved PD status, regardless of the contribution of the missing lesion.

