## 14. Endpoints definition

### 14.1. Progression-free survival

It is defined as the time from the date of randomisation until documented progression or death, if progression is not documented. Censoring will occur at the last tumour assessment only if patient is lost to follow-up.

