- o In all other cases, the patient will be censored at the date of randomization plus 1 day.

Reporting conventions

Regarding the estimates presented in the report, the following rules will be adopted:

- P-values ≥0.001 will be reported with three decimal places
- P-values >0.010 will be reported with two significant demical digits
- P-values less than 0.001 will be reported as "<0.001"
- Means, medians, 95% confidence limits (Cis), quantiles, and any other summary statistics, will be reported with one decimal digit
- Hazard ratios (HRs) and their 95% CI's will be reported to two decimals
- Estimated parameters, not on the same scale as raw observations (e.g. regression coefficients) will be reported to three significant figures.

Multiple recordings of an event for the same patient

There are some cases where a patient may experience the same event (AE/SAE) more than once. In such cases, the event will be counted only once for the calculation of the total number of events reported for the overall safety cohort.

Presentation of results

The results will be presented through tables and figures. A summary of the results will also accompany the main report. First, a short synopsis of the results will be presented through bullets, where only the most important findings will be shown. Following that, a more detailed description of the results will be provided, sectioned in the following order:

- Patient accrual and baseline characteristics
- Follow-up and Treatment administration

- Efficacy analysis
- Safety analysis

All tables and figures will be included in an appendix.

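### The primary PFS analysis accepts a non-evaluable last scan as the censoring date and leaves the evaluable-only rule to a sensitivity analysis

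*SAP*

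**What the plan says.** SAP 2.2.1 gives the primary rule: "Censoring (patients without progression/death) for PFS will occur at the last tumour assessment". The next sentence, introduced as a sensitivity analysis, adds that "if the last tumour assessment is «Non evaluable», censoring will occur to the more recent tumour assessment where an overall evaluable result is recorded". Read together, the two sentences leave the date of an NE assessment in place as the primary censoring date.

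Protocol 14.1 does not change this. It says "Censoring will occur at the last tumour assessment only if patient is lost to follow-up", which limits who is censored this way but, like the SAP, sets no evaluability condition.

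Protocol 13.3 (Table 15 and its footnote) says what NE means. One case is a partly measured scan: "If only a subset of lesion measurements are made at an assessment, usually the case is also considered NE at that time point". The other is a time point without imaging: "When no imaging/measurement is done at all at a particular time point, the patient is not evaluable (NE) at that time point".

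SAP section 5 (missing data, incomplete tumour assessment) deals with patients who have no on-study assessment. Early death or early clinical progression counts as an event; otherwise, "In all other cases, the patient will be censored at the date of randomization plus 1 day". It does not mention patients who were assessed but only with NE results.

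**The concern.** Censoring at a date asserts that the patient was known to be progression-free up to that date. An NE assessment does not support this in full, yet the interval that ends in it enters the risk set as event-free time. The SAP is stricter with a patient who has no on-study assessment and no early event, who gets 1 day of follow-up. A patient whose single assessment is NE falls outside that rule and is credited up to the NE date.

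At stake is the only primary endpoint. After the early closure of accrual, SAP 1.4.2 rests the confirmatory test on PFS alone with 81 events. The trial is open-label and progression is read by the local radiologist. If NE results were more frequent in one arm, the extra event-free time would favour that arm. The documents allow for such an imbalance but give no evidence of one.

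**Working it through.** **1. The plan's own figure.** Inputs from SAP 1.4.1 and 1.4.2: 1:1 allocation, one-sided alpha 0.05, power 80%, medians 13.1 and 22.8 months.

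Schoenfeld: events = 4(z₀.₉₅ + z₀.₈₀)² / (ln HR)².

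- HR = 13.1/22.8 = 0.5746: 4 × (1.645 + 0.842)² / 0.554² ≈ 80.5, so 81. This matches the SAP.
- Rounded HR of 0.57: 79.

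The choice of censoring rule moves only censoring dates. It neither adds nor removes events, so 81 stands under either rule.

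**2. Follow-up credited per affected patient.** From the CT schedule in Protocol 13.2, at 52.18/12 = 4.348 weeks per month, one NE scan at the end of follow-up adds at least:

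- up to week 81: 9 weeks = 2.1 months
- weeks 93 and 105: 12 weeks = 2.8 months
- weeks 131 to 209: 26 weeks = 6.0 months

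**3. Effect on the hazard ratio, by simulation.** From the documents: the medians, the scan schedule and the 81-event target. Assumed, because the documents do not give them: 150 randomised, uniform accrual over 40 months, exponential PFS, and an independent NE probability per scan in each arm.

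Progression is recorded at the first evaluable scan after it occurs. The cut-off is the 81st true event, but not before accrual ends. There were 1,500 trials per scenario, each analysed under both rules with a Cox model and a one-sided Wald test. Under the evaluable-only rule, patients with no evaluable scan are censored at about 1 day. HR is experimental over observation.

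| True HR | NE per scan, obs./exp. | HR, current rule | HR, evaluable-only | Rejection, current | Rejection, evaluable-only |
|---|---|---|---|---|---|
| 1 | 5% / 5% | 0.998 | 0.998 | 3.5% | 3.5% |
| 1 | 10% / 10% | 0.998 | 0.999 | 4.7% | 4.3% |
| 1 | 20% / 20% | 1.001 | 1.001 | 3.1% | 3.1% |
| 1 | 5% / 15% | 0.977 | 0.989 | 4.9% | 4.4% |
| 1 | 5% / 30% | 0.930 | 0.969 | 7.9% | 5.7% |
| 1 | 30% / 5% | 1.081 | 1.038 | 1.6% | 2.8% |
| 0.5746 | 10% / 10% | 0.590 | 0.590 | 72.2% | 72.3% |
| 0.5746 | 5% / 15% | 0.578 | 0.586 | 75.7% | 73.5% |
| 0.5746 | 5% / 30% | 0.541 | 0.565 | 84.2% | 78.7% |
| 0.5746 | 30% / 5% | 0.638 | 0.611 | 61.4% | 68.5% |

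Differences between rules:

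- Equal NE rates: at most 0.001.
- 5% versus 15%: 0.989 − 0.977 = 0.012 under the null and 0.586 − 0.578 = 0.008 under the alternative.
- 5% versus 30%: 0.969 − 0.930 = 0.039 and 0.565 − 0.541 = 0.024.

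Reversing the imbalance reverses the direction. Across scenarios, the time credited without an evaluable scan averaged about 3 to 4 months per affected patient.

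**4. Precision.** Each mean log HR has a simulation error of about (2/√81)/√1500 = 0.006, and a rejection rate near 5% has one of √(0.05 × 0.95/1500) = 0.6 percentage points. The two rules are compared on the same trials with the same events, so the differences between them are more precise than the separate values.

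**5. What the simulation simplifies.** It does not let an NE scan reveal progression, it gives every NE scan a recorded date, and it does not model deaths separately. These choices probably overstate the effect at a given NE rate.

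**The case against.** The strongest reply is that the SAP already plans the stricter rule. Both results will be reported and any dependence on NE scans will be visible. The SAP also keeps the protocol's reference to the last tumour assessment as primary, and nothing in the documents contradicts that choice. This stands: the point is only which of two planned analyses carries the confirmatory test.

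Three stronger readings are tempting, and the documents do not support them.

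- A reader might infer that an NE assessment says nothing about progression. In Table 15 the NE row requires that non-target lesions have not progressed and that there is no new lesion. Progression can still be called from the lesions that were measured. A partly measured scan therefore carries partial information.
- A reader might infer from "When no imaging/measurement is done at all at a particular time point, the patient is not evaluable (NE) at that time point" that a missed scan is counted as progression-free follow-up. That footnote labels a scheduled time point. The case report form schedule (Protocol 17.1) ties the post-randomisation tumour assessment form to the date of a CT, so a missed scan normally leaves no date to censor at.
- A reader might infer that the primary result is biased. CT schedules are the same in both arms and no NE rate is given. A visible rise in the one-sided error (7.9% against 5.7%) appears only at the assumed 5% versus 30%.

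It is also fair to say that the evaluable-only rule does not remove all distortion. At 5% versus 30% under the null, the HR is still 0.969, because progression is detected later in the arm with more NE scans.

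**Conclusion.** The point holds as a minor one. The primary PFS rule accepts an NE last assessment as the censoring date and so counts at least one scan interval in which progression was not fully excluded. The expected effect is negligible if NE rates are similar in the two arms, about 0.01 on the HR at 5% versus 15%, and about 0.02 to 0.04 at an extreme 5% versus 30%. The direction favours the arm with more NE scans. These sizes depend on the assumed NE rates, number randomised and accrual period, none of which the documents supply. The case for change is that the better-supported rule is already written down and costs almost nothing to make primary.

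**What to change.** In SAP 2.2.1, exchange the two rules before the final analysis. Censor patients without progression or death at the last evaluable tumour assessment in the primary analysis, and keep censoring at the last assessment of any kind as the sensitivity analysis.

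In SAP section 5, add that patients without an event whose only post-randomisation assessments are NE are censored at randomisation plus 1 day, as already planned for those with no on-study assessment. Without this, the latest evaluable scan could be the one taken up to 14 days before randomisation, which would give a negative PFS time.

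The cost is one or two sentences and slightly shorter follow-up in some censored patients. Both analyses are already pre-specified, and the 81-event requirement and the analysis trigger stay as they are.

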2.2.2 Secondary endpoints

Secondary endpoints include OS, ORR, TTF and adverse events (AEs) graded according to CTCAE v4.0. More specifically:

- OS is defined as the time from the date of randomization until death from any cause.
 Censoring (patients without death) for OS will occur at the last follow-up date.
- ORR is defined as the rate of best overall response (complete or partial response)
 according to RECIST 1.1 criteria across all assessment time-points, during the period from
 randomization to termination of trial treatment. Of note, the determination of ORR will be
 restricted to patients who have not attained a CR during chemo-radiotherapy.
- TTF is defined as the time from the date of randomization to treatment failure for any reason (including progression of disease, treatment toxicity, refusal, lost to follow-up and death). Censoring for TTF (patients without failure) will occur at the last-follow-up date.
- Toxicity, defined as adverse events classified according to CTCAE v4.0.

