### **5.4. Secondary endpoints**

5.4.1. Objective response determined by RECIST 1.1

5.4.2. Time to treatment failure

5.4.3. Adverse events graded according to CTCAE V4.0

For definitions, see section 14.

[figure not shown]

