### 14.4. Time to treatment failure

Defined as time from the date of randomisation to discontinuation of treatment for any reason (including progression of disease, treatment toxicity, refusal and death). Censoring will occur at the last follow-up date.

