## **18.4. Evaluation of primary and secondary objectives**

The total study duration will be approximately 7.5 years including the 36 months recruitment period. The primary analyses on PFS and OS will be performed overall and stratified by radiotherapy schedule. An intent to treat primary efficacy analysis will be performed, including all eligible patients randomised (= efficacy cohort).

PFS and OS will be estimated by the Kaplan Meier method and compared between the two treatment arms by a stratified logrank test. In addition, stratified (by the randomisation stratification factors) and multivariate Cox models will be used for exploring the association of PFS and OS with treatment in the presence of prognostic factors.

The two treatment groups will also be compared with respect to secondary efficacy and tolerability endpoints. No multiplicity adjustment will be performed for these analyses.

Time to treatment failure (TTF) will be estimated by the Kaplan Meier method and compared between the two treatment arms based on the logrank test stratified by the randomisation stratification factors. Cox proportional hazards regression adjusting for prognostic factors will also be performed for this secondary endpoint.

All time-to-event endpoints will be presented and evaluated from date of randomisation, with secondary presentation from date of enrolment.

Clinical efficacy will be further described by objective response rate (ORR, defined as percentage of patients reaching a complete or partial response) based on RECIST 1.1 response

criteria. The determination of ORR will be restricted to patients who have not attained a CR during chemo-radiotherapy.

Assessment of response by immune-related response criteria based on RECIST 1.1 will be explored post-hoc, centrally, in the randomised consolidation phase of the trial.

Safety and the tolerability of the nivolumab plus ipilimumab consolidation therapy will be described by tabulation of the CTCAE Version 4 grade. The safety cohort will encompass all patients who have received at least 1 dose of IMP treatment plus all patients randomised to observation.

The correlation of biological markers with OS and PFS will be evaluated by univariate and multivariate Cox proportional hazards regression.

OS analysis will also be performed for the full cohort of 325 patients for descriptive purposes. The survival time for the full cohort will be defined as the time from enrolment into the trial until death.

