2.2.3 Exploratory endpoints

 TTD is defined as the time from the randomization to treatment discontinuation for any reason (including progression of disease, treatment toxicity, refusal, lost to follow-up and death). Censoring for TTD (patients on treatment or completed treatment), will occur at the last-follow-up date

 DoR is defined as the time from the documentation of tumour response (either partial or complete response) to disease progression or death. Censoring will occur at the last tumour assessment with response other than progression.

2.2.4 (Serious) Adverse Events

Adverse Events (AEs)

The main criterion for treatment tolerability is the occurrence of toxicities and adverse events. The severity and causality will be classified according to the NCI CTCAE version 4 (http://evs.nci.nih.gov/ftp1/CTCAE/About.html).

An adverse event is defined as any untoward medical occurrence that occurs from the day of enrolment in the Remote Data Entry (RDE) until 100 days after the final dose of IMP regardless of whether it is considered related to a medication. The relation of the adverse event with the administered trial treatment has to be indicated as: unrelated, unlikely, possible, probable or definite. In addition, any known untoward event that occurs subsequent to the adverse event reporting period that the investigator assesses as possibly related to the protocol treatment should be considered an adverse event.

Immune-related Adverse Events (irAEs)

The following adverse events are of special interest and must be documented after randomization in both treatment arms:

CTCAE Version 4.0 system organ class / preferred terms:

Nervous system disorders:

- Peripheral motor neuropathy
- Peripheral sensory neuropathy
- Meningismus
- Limbic Encephalitis
- Nervous system disorders Other, specify (Guillain-Barré, myasthenia gravis, aseptic or non-infectious meningitis)

Skin and subcutaneous tissue disorders:

- Stevens-Johnson syndrome
- Toxic epidermal necrolysis
- Bullous dermatitis
- Rash acneiform
- Rash maculo-papular
- Pruritus
- Skin and subcutaneous tissue disorders Other, specify

Gastrointestinal disorders:

- Colitis

- Diarrhea
- Colonic perforation
- Small intestinal perforation
- Gastric perforation
- Gastrointestinal disorders Other, specify

Hepatobiliary disorders:

- Hepatic failure
- Hepatitis viral
- Drug-induced liver injury (DILI)

Investigations:

- Alanine aminotransferase increased
- Aspartate aminotransferase increased

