4.2 Follow-up information and Treatment administration

Follow-up time of the patients will be presented as:

- Median follow-up (FU) of the randomized patients (overall and by treatment arm) along with the respective interquartile range (IQR) and the number (%) of patients that are still on FU.

¹ Note: This table includes the number of patients registered in the database and characterized as ineligible, but this does not represent the full set of screened patients since, it is not mandatory by the protocol to enter in the database all screened patients, even if not eligible.

- A Kaplan-Meier (K-M) plot will be provided for a graphical representation of follow-up time, overall and by treatment arm.

Treatment information will be summarized first for the chemo-radiotherapy phase and then for the randomization phase overall and separately by treatment arm. More specifically the following information will be presented:

- No. of patients enrolled (under protocol AM1)
- No. of patients stopped the trial before starting any treatment
- No. of patients started chemo-radiotherapy treatment
- No. of treatment failures during chemo-radiotherapy treatment (including failure reasons)
- No. of patients completed chemo-radiotherapy phase
- No. of patients not completed PCI for specific reasons
- No. of patients received (and completed) PCI after chemo-radio therapy phase
- No. of unrandomizable patients
- No. of randomized patients (by arm)
- No. of patients that started treatment with the IMP
- No. of patients that completed treatment
- No. and reasons of treatment failures during randomization phase (by arm)
- No. of patients that completed treatment and they experienced a failure afterwards.
- 6-month, 1/2-year TTF rate (%) and median TTF estimates, along with corresponding 95%CI and log-rank test p-value for comparison of the two treatment arms
- A Kaplan Meier curve for TTF by treatment arm
- For those patients who progressed, information on further lines of treatment (if available) will be provided by treatment arm.

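### The SAP redefines the secondary endpoint time to treatment failure without saying so: an undefined failure event, loss to follow-up scored as an event, and a weaker analysis than the protocol specifies

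*SAP*

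**What the plan says.** **Protocol.** Section 5.4 lists TTF as a secondary endpoint ("5.4.2. Time to treatment failure"). Section 14.4 gives the event: "Defined as time from the date of randomisation to discontinuation of treatment for any reason (including progression of disease, treatment toxicity, refusal and death"). The censoring rule follows: "Censoring will occur at the last follow-up date". Section 18.4 requires the arms to be compared "based on the logrank test stratified by the randomisation stratification factors", and adds Cox regression adjusted for prognostic factors.

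**SAP.** Section 2.2.2 keeps TTF as secondary: "TTF is defined as the time from the date of randomization to treatment failure". Its list of causes adds loss to follow-up to those in the protocol: "reason (including progression of disease, treatment toxicity, refusal, lost to follow-up and death"). Patients without failure are censored at last follow-up. Section 2.2.3 introduces an exploratory endpoint that the protocol does not have: "TTD is defined as the time from the randomization to treatment discontinuation for any" reason, with the same list including loss to follow-up. Patients still on treatment, or who completed it, are censored.

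SAP 4.2 reports TTF rates, the median, a Kaplan-Meier curve and a log-rank p-value, with no mention of stratification and no Cox model. The same section tabulates "No. of patients that completed treatment and they experienced a failure afterwards". SAP 4.3.2 gives exploratory TTD a stratified log-rank test.

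**The concern.** A reader of the final report will take TTF to be the protocol's secondary endpoint, but three things have changed under that name: the event, the status of patients lost to follow-up, and the analysis. The notes in SAP 1.1 and the account of design changes in SAP 1.4.2 report the move of OS to secondary status and the new alpha. Neither mentions TTF.

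The loss-to-follow-up rule matters most. Loss to follow-up means that the outcome was not observed; it is not itself an outcome of treatment. Scoring it as failure makes the TTF comparison depend on how well each arm is followed, in an open-label trial where one arm attends for infusions and the other does not.

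**Working it through.** The documents give no figure for TTF, so there is none to reproduce. The check is a comparison of the texts, followed by a scale calculation.

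**Step 1: the definitions side by side**

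| | Protocol TTF (14.4, 18.4) | SAP TTF (2.2.2, 4.2) | SAP TTD (2.2.3, 4.3.2) |
|---|---|---|---|
| Tier | Secondary | Secondary | Exploratory |
| Event | Discontinuation of treatment | Treatment failure, undefined | Discontinuation of treatment |
| Loss to follow-up | Not listed | Listed as event | Listed as event |
| Completers | Not addressed | Not addressed | Censored |
| Log-rank | Stratified | Not specified | Stratified |
| Adjusted Cox model | Yes | None | None |

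SAP 4.4 promises subgroup estimates for the secondary efficacy endpoints in general. That does not replace the adjusted model in Protocol 18.4.

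**Step 2: are failure and discontinuation the same thing in the SAP?** The SAP lists TTF and TTD separately and censors them differently: TTD censors completers, while TTF censors only patients without failure. SAP 4.2 counts failures after completed treatment, and these cannot be discontinuations. The natural reading is that a patient who completes treatment and later progresses is an event for TTF and censored for TTD. The SAP does not state this.

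**Step 3: how is a lost patient coded?** Under SAP 2.2.2 a lost patient is an event by the list of reasons, yet the censoring date is also last follow-up. No event date is given for such patients. Protocol 14.4 leaves loss off its list and censors at last follow-up. For PFS, Protocol 14.1 explicitly makes loss to follow-up a reason for censoring.

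**Step 4: scale**

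Inputs: 3% loss after randomisation and 260 randomised (Protocol 18.3); 1:1 allocation, so 130 per arm (SAP 1.4.1); 60% of an arm with TTF events otherwise (an assumption found in neither document).

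- Patients whose status could change: 0.03 × 260 = 7.8, about 8.
- Baseline events per arm: 0.60 × 130 = 78.
- Even split: 7.8 / 2 = 3.9 extra events per arm. If 60% holds in both arms, each count is multiplied by (78 + 3.9) / 78 = 1.05, so the hazard ratio factor is 1.05 / 1.05 = 1.00. Unequal event rates would move it only slightly.
- All losses in the observation arm: 7.8 / 130 = 6% of that arm. Its events are multiplied by (78 + 7.8) / 78 = 1.10. To first order the hazard ratio is multiplied by 1 / 1.10 = 0.91, a fall of about 9%.
- All losses in the experimental arm: the factor is 1.10, a shift the other way.

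The 3% and the 260 are planning figures from before accrual closed early. The SAP gives no number randomised after closure.

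**The case against.** The case for the SAP has real content.

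- **The protocol definition is incomplete.** The observation arm receives no treatment, so discontinuation has no stated meaning there, although Protocol 18.4 requires a between-arm test. Failure can at least be applied in both arms. Protocol 10.11 also lists completing a year of maintenance among the events that end treatment, so discontinuation for any reason might include planned completion. This stands: restoring Protocol 14.4 word for word would not be enough.
- **The protocol's list of reasons is open.** It is introduced as a list of inclusions, and the TTF censoring sentence does not name lost patients. This stands in part. Censoring is the natural reading rather than explicit text, but the SAP goes further and names loss as an event.
- **Omitting the word stratified is not the same as choosing an unstratified test.** True. But SAP 4.2 leaves the test open for a secondary endpoint, SAP 4.3.2 closes it for an exploratory one, and the Cox model is absent altogether.
- **Discontinuation is still analysed, as TTD.** True, so little information is lost.

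A reader might infer that the protocol's definition was simply moved to TTD. It was not: TTD also counts loss to follow-up and sets its own rule for completers.

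A reader might also infer that the rule favours the experimental arm, because clinic visits are sparser under observation. The documents do not support that. Both arms have CT every 9 weeks up to 18 months (Protocol 13.2), and nothing in either document indicates higher loss in one arm.

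**Conclusion.** The SAP departs from Protocol 14.4 and 18.4 for a secondary endpoint and does not acknowledge it. It substitutes an undefined event, scores loss to follow-up as failure in both TTF and TTD, and specifies less analysis than the protocol does. This is more than missing detail, because the loss-to-follow-up rule is written down and would be programmed as it stands.

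The likely numerical effect is small. At the planning assumptions about 8 patients could change status, with almost no effect on the hazard ratio if losses are balanced. The 9% shift is a constructed worst case that rests on wholly one-sided loss and an assumed 60% event rate, and the opposite imbalance would reverse its sign. It should not be read as an estimate of bias. Primary PFS is unaffected, and Protocol 18.4 applies no multiplicity adjustment to secondary endpoints. The point should be corrected before the analysis, because the report would otherwise show a different quantity under the protocol's name.

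**What to change.** 1. In SAP 2.2.2 and 2.2.3, remove loss to follow-up from the TTF and TTD events and censor those patients at last follow-up.
2. Tie secondary TTF to the event in Protocol 14.4. State how patients who complete treatment are handled and what counts as the event in the observation arm.
3. If a broader failure measure is wanted, define it and report it under its own exploratory name.
4. In SAP 4.2, analyse TTF with the stratified log-rank test and adjusted Cox model of Protocol 18.4.
5. Record the departure and its reason in the SAP, for example in 1.1 or 2.2.2. Section 1.4.2 is less suitable because it covers changes caused by accrual closure.

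The cost is a few lines of SAP text, recoding of the event indicators and one added model. Protocol Table 16 already provides forms for end of treatment, follow-up, and withdrawal or loss to follow-up, so no new data are needed.
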